- H0: Patients who receive LA infiltration in two stages (pre-incision with lidocaine+adrenaline and pre-extubation with ropivacaine) do not have less postoperative pain.
- H1: Patients who receive AL infiltration in two stages (preincisional with lidocaine+adrenaline and pre-extubation with ropivacaine) have less postoperative pain.

OBJECTIVES

The main objective of the study is the evaluation of the effect of a peripheral preincisional minor nerve block with the use of a single local anesthetic (lidocaine), compared with the same nerve block in two times with different local anesthetics (lidocaine-preincisional and ropivacaine-pre-extubation), on the postoperative pain of patients undergoing elective bimaxillary osteotomy, evaluated by means of the visual analogue scale (VAS) of pain in the immediate postoperative period (2 hours postoperatively). The secondary objectives of the study are: the comparison of pain at 4, 8 and up to 18 hours after surgery, the comparison of the opioid use of rescue (intravenous methadone milligrams) in the postoperative period of bimaxillary osteotomy in the two groups of patients in the immediate postoperative period in resuscitation (2 hours postoperatively) and in the hospitalization floor (18 hours postoperatively), comparing the incidence of postoperative nausea and vomiting (PONV) in the immediate postoperative period in resuscitation (2 hours postoperatively) and up to 18 hours after the surgery in the two groups of patients, and the registry of complications derived from the two infiltrations.

MATERIAL AND METHODS

Study design

The investigators propose a double-blinded prospective comparative experimental study (patient and nurse). After the approval of the ethics committee of our hospital and the signed consent from each of the patients in the study, patients will be scheduled for bimaxillary osteotomy and will be randomly and prospectively assigned to one of the two groups with a plan to register up to 52 patients. Patients will not know the group that they have been assigned consecutively; and both the postoperative resuscitation nurses and the hospitalization nurses who will perform VAS records, opioid consumption, PONV and postoperative complications, will also be unaware of the analgesic treatment that the patient has received in the operating room. Patients will be assigned randomly to one group or another:

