- Control group: patients undergoing elective bimaxillary osteotomy who receive a preincisional infiltration of lidocaine and adrenaline.
- Study group: patients undergoing elective bimaxillary osteotomy who receive two infiltrations (firstly pre-incision with lidocaine and adrenaline, secondly pre-extubation with ropivacaine).

Population

The source and mechanism of subject selection is a convenience sample, with consecutive recruitment in our clinic at the Maxillofacial Institute of Teknon Medical Center.

The criteria for the selection of subjects is the following. The inclusion criteria are patients who undergo scheduled bimaxillary surgery. The exclusion criteria are: the refusal to participate in the study, patients who are scheduled for bimaxillary surgery together with another complementary surgical procedure (such as mentoplasty, rhinoplasty, blepharoplasty), age <18 years, reinterventions, urgent surgeries, allergies to local anesthetics, allergies to anti-inflammatories agents, allergies to opioids, American Society of Anesthesiology Physical Status Examination System (ASA) >3.

Procedure/Intervention

Patients will be received in the surgical area and a venous access line will be placed where premedication (Midazolam 2mg/intravenous) and antibiotic prophylaxis (amoxicillin-clavulanic 2g/intravenous or Clindamycin 600mg/intravenous in case of patients allergic to beta-lactams) will be administered. They will be monitored in the operating room (plasma oxygen saturation, electrocardiogram, non-invasive blood pressure -NIBP-, Bispectral index, Train of four TOF - CUFF neuromuscular monitor) and general intravenous anesthesia will be carried out (anesthetic induction: fentanyl 2mcg/kg/intravenous, propofol 2mg/kg/intravenous, rocuronium 0.6mg/kg/intravenous; and anesthetic maintenance: sevoflurane Minimum Alveolar Concentration (MAC) 1.2 and remifentanil (RMF) Target Controlled Infusion (TCI) - Effective Concentration 2ng/ml). After the nasal intubation of the patient, the administration of the LA will proceed by the following routes:

- Control Group: the surgeon will proceed with pre-incisional infiltration with lidocaine and adrenaline at the intraoral and intranasal submucosal level in the maxilla and jaw to block the terminal branches of the maxillary and mandibular nerve.

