agent (tranexamic acid 15mg/kg/intravenous), gastric protection (ranitidine 50mg/intravenous) , antiemetic agent (ondansetron 4mg/intravenous) and analgesics (paracetamol 1g/intravenous, dexketoprofen 50mg/intravenous, diclofenac 75mg/intramuscular) and ketamine in subanesthetic doses (ketamine 20mg/intravenous in the induction and ketamine 40mg/intravenous slow intraoperative administration). The mechanical ventilation by controlled volume (6ml/kg) will be adjusted to maintain a CO₂ at the end of expiration around 32-38mmHg. In the intraoperative period, in cases of changes in basal NIBP equal to or greater than 20%, remifentanil will be increased/reduced in TCI 0.2ng/ml. If NIBP increases last longer than 5 minutes, administration of remifentanil bolus 2mcg/intravenous will proceed. If abrupt drops of the NIBP will proceed to stop the TCI RMF. Patients will be extubated in the operating room after removal of pharyngeal tamponade, gastric aspiration and reversal of neuromuscular relaxation and recovery of protective airway reflexes. In the postoperative period, a VAS value greater than 3 will be considered as insufficient pain control and rescue analgesia will be administered (first anti-inflammatory metamizole 2g/intravenous, and second opioid methadone 2mg/15minutes/intravenous in resuscitation, up to a total of 10mg/intravenous in the 2hours stay in resuscitation, and methadone 5mg/6hours/subcutaneous in hospital ward 2-18hours post-operative).

Definition of the variables

Definition of the variables

- demographic data: age (years), sex (man/woman)
- anthropometric data: weight (kg), height (cm)
- comorbidities: free text
- ASA (American Society of Anesthesiologists) physical status classification system: 1-3
- Temporary structure of evaluations:
 - Post-operative pain measured with the Visual Analogue Scale (VAS 0-10): at 2, 4, 8 and 18hours postoperatively.
 - Total intraoperative opioid dose (TCI-RMF effect concentration).
 - Total intravenous dose of opioids-methadone in the postoperative period (mg) in resuscitation (2hours postoperative) and subcutaneous methadone in hospitalization (2-18hours postoperative).
 - Presence of PONV at 2, 4, 8 and up to 18hours postoperatively.
 - Complications derived from infiltration with lidocaine and adrenaline
 - Complications derived from infiltration with ropivacaine

CALCULATION OF THE SAMPLE AND STATISTICAL ANALYSIS

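### The ropivacaine complications item cannot be read against a control rate, and the nurses' cause-neutral complications record is never made a variable or compared by arm

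*Combined protocol and SAP*

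**What the plan says.** The section Definition of the variables lists two complications items: "Complications derived from infiltration with lidocaine and adrenaline" and "Complications derived from infiltration with ropivacaine". Neither has an event list, time points or an attribution rule.

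Both groups receive the pre-incision lidocaine and adrenaline. Only the study group are patients "who receive two infiltrations (firstly pre-incision with lidocaine and adrenaline, secondly pre-extubation with ropivacaine". The control group has a single infiltration, and no sham second infiltration is described (Study design; Pharmacological treatments; Calculation of the sample and statistical analysis).

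Objectives words the secondary aims on pain and rescue opioid as comparisons, and likewise PONV: "comparing the incidence of postoperative nausea and vomiting (PONV". For complications it asks only for "the registry of complications derived from the two infiltrations".

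Study design adds a cause-neutral source. The resuscitation and ward nurses are those "who will perform VAS records, opioid consumption, PONV and postoperative complications, will also be unaware of the analgesic treatment". That record of complications carries no cause qualifier and covers both groups, but it does not reappear in the variable list. By contrast, PONV is listed without reference to cause and with fixed times: "Presence of PONV at 2, 4, 8 and up to 18hours postoperatively".

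The statistical section gives a sample size and a t test for VAS at 2 hours. It gives no analysis or table for complications.

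**The concern.** The planned difference between the groups is the second infiltration. The natural safety question is what that infiltration adds in complications, and randomisation allows it to be answered by counting the same events in both groups.

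An item that applies only to the study group cannot answer it. Some patients will have events after this surgery whichever group they are in. In the study group such an event can be entered under ropivacaine; in the control group it cannot. A reader who sees a count under ropivacaine then has no control rate beside it, and cannot tell drug effect from background.

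The source of attribution is also unclear. Nurses unaware of treatment cannot assign an event to ropivacaine, and the documents do not say who does. The nurses' record and the two listed items are therefore different things, and nothing connects them.

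**Working it through.** **Which item applies to which group**

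| Item | Control | Study | Between-arm contrast |
|---|---|---|---|
| Attributed to lidocaine and adrenaline | applies | applies | possible, but depends on attribution |
| Attributed to ropivacaine | not applicable | applies | none |
| Nurses' postoperative complications, no cause stated | recorded | recorded | possible, but not a listed variable and not tabulated |

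**The denominator.** The plan's figure is 52 patients, 26 per group, for a 1-point VAS difference, SD 1.25 (d = 1/1.25 = 0.8) and 80% power. A two-sided independent-samples t test at alpha 0.05 gives 26 per group, with achieved power 80.7%. The figure reproduces and is not in dispute; 26 per group is used below.

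**Illustration of the attributed item.** Assume no true difference between arms. Let b be the background risk per patient of an event after the second infiltration, and s the share of such events in the study group that are attributed to ropivacaine. Both are assumptions, because the documents give neither.

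- Expected study-arm count = 26 × b × s.
- Chance of at least one = 1 − (1 − b·s)^26.

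At b = 5%:

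- s = 0.1: expected 0.13; 1 − 0.995^26 = 12%.
- s = 0.5: expected 0.65; 1 − 0.975^26 = 48%.
- s = 1: expected 1.3; 1 − 0.95^26 = 74%.

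Chance of at least one across a range of b:

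| b | s = 0.1 | s = 0.5 | s = 1 |
|---|---|---|---|
| 1% | 2.6% | 12% | 23% |
| 2% | 5% | 23% | 41% |
| 5% | 12% | 48% | 74% |
| 10% | 23% | 74% | 94% |
| 20% | 41% | 94% | 99.7% |

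With b held fixed and no true effect, the result moves with s alone. A cause-neutral count has the same expected value, 26 × b, in both arms whatever s is.

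**Precision of the cause-neutral count.** The approximate 95% half-width for the difference in proportions, with the same rate b in both arms, is 1.96 × √(2b(1 − b)/26):

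- b = 5%: 0.118
- b = 10%: 0.163
- b = 20%: 0.217

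That is about 12 to 22 percentage points. This simple interval has zero width at 0/26 against 0/26, so it should not be used for reporting. The Newcombe interval gives ±0.129 at 0/26 in both arms, ±0.154 at 1/26 in both, and ±0.215 at 5/26 in both.

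**The case against.** The plan is consistent with itself. The objective is a registry by infiltration, and the variable list has one item per infiltration. A reader might infer that the registry fails or contradicts its objective; the documents do not support that. A between-arm safety estimate is something the plan never promised.

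A reader might also infer that complications go unrecorded in controls. Study design says otherwise: blinded nurses record them in both groups. What is missing is a line in the variable list and a table. The missing table is not peculiar to complications either, since PONV and rescue opioid also have no stated analysis method.

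The larger chances in the table (94%, 99.7%) need high assumed background rates and half or all of the events blamed on ropivacaine, although a second item is available for attribution. They should not be taken as forecasts.

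The events during surgery that the plan names do not fit the mechanism. Limitations speaks of arrhythmias during the operation, and Procedure/Intervention and Pharmacological treatments deal with blood-pressure falls in the intraoperative period. Ropivacaine is given once surgery is complete, so these events precede it. Only the later period is relevant.

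Finally, the Introduction's remark that toxicities add up is made while warning against maximum doses of two combined agents. It is not an assessment of these two sequential infiltrations and does not show that this regimen is hazardous.

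All of this stands, and it limits the point. What remains is that the one item specific to the added treatment gives a count dependent on attribution and without a control rate, while a cause-neutral record that could give one is left undefined.

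**Conclusion.** The point holds as a gap in definition and tabulation for a secondary outcome. The ropivacaine item gives no between-arm estimate of what the second infiltration adds, and the plan does not turn the nurses' existing record into one.

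The size is modest and rests on assumed rates. At 5% background after the second infiltration and no true difference, the chance of at least one labelled ropivacaine complication runs from about 12% to 74% as the attributed share goes from 10% to all. At 1% to 2% background with a 10% share it is 5% or less.

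A reader might go further and conclude that the trial's main result is at risk. Nothing here supports that: the 2-hour VAS analysis, the t test and N = 52 are untouched. The cause-neutral count would itself be descriptive only, because 26 per group leaves wide intervals. The change is optional, but it has to be made before the first patient if the same event list is to be applied to everyone.

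**What to change.** Keep the two attributed items as the registry. Add one variable, postoperative complications regardless of cause, as follows.

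- **Event list.** The same short list plus an other category in both groups, fixed before the first patient. Show respiratory depression as its own line: the Introduction ties it to opioids, so less opioid use could lower it in the study group and offset harm in a pooled count.
- **Recording.** The blinded nurses enter it at the existing 2, 4, 8 and 18 hour assessments.
- **Window.** The headline count covers only the period after surgery is completed, when the arms differ. Events during surgery precede ropivacaine and are not counted. Events in the operating room after completion of surgery come from the existing team and the monitoring already in place ("They will be monitored in the operating room (plasma oxygen saturation, electrocardiogram, non-invasive blood pressure"). These entries are unblinded and are shown separately.
- **Attribution.** Any assignment to an infiltration is made after the 18 hour record is complete, by an existing investigator who does not record VAS.
- **Reporting.** n/26 by randomised group, with a Newcombe 95% interval for the difference, descriptively and without a test.

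The cost is a slightly longer form at four existing assessments, agreement on the event definitions, a brief operating-room entry and a later attribution step. No extra patients, visits or staff are needed. The drawback is imprecision: with half-widths of roughly 12 to 22 points at assumed rates of 5% to 20%, the comparison can put counts in context but will rule out little.

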- Study Group: the surgeon will proceed firstly with pre-incisional infiltration with lidocaine and adrenaline and secondly with pre-extubation infiltration with ropivacaine at the intraoral and intranasal submucosal level in the maxilla and jaw to block the terminal branches of the maxillary and mandibular nerve.

PHARMACOLOGICAL TREATMENTS

- Control group: Infiltration performed by the surgeon at the intraoral and intranasal submucosal level in the maxilla and jaw (blockage of terminal branches of the maxillary and mandibular nerve) after intubation and previous to surgical incision.
A total of 50ml of the following preincisional mixture is infiltrated: $\frac{1}{2}$ blister 1mg/ml Adrenaline + 1blister 10ml Lidocaine 2% in physiological saline 100ml.
- Study group: Two infiltrations. Firstly, infiltration performed by the surgeon at the intraoral and intranasal submucosal level in the maxilla and jaw (blockage of terminal branches of the maxillary and mandibular nerve) after intubation and previous to surgical incision. A total of 50 ml of the following preincisional mixture is infiltrated: $\frac{1}{2}$ blister 1 mg/ml Adrenaline + 1blister 10ml Lidocaine 2% in physiological saline 100ml.
Secondly, infiltration performed by the surgeon at the intraoral and intranasal submucosal level in the maxilla and jaw (blockade of terminal branches of the maxillary and mandibular nerve) before extubation. A total of 20 ml of ropivacaine 0,37%.

Previous to the surgical incision, fentanyl 0.5mcg/kg/ev will be administered again to all patients and infusion of TCI of RMF at 2 ng/ml effect concentration will be initiated. It will be administered intraoperative to all patients as adjuvant therapy, as long as there is no contraindication, corticotherapy (methylprednisolone 15mg/kg/intravenous), antifibrinolytic

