The sample selection method foresees the consecutive allocation of patients to two groups:

1. Control Group: a single pre-incision infiltration of LA lidocaine+adrenaline
2. Study Group: two infiltrations with pre-incision lidocaine+adrenaline and pre-extubation with ropivacaine.

The degree of pain is assessed using a visual analog scale (VAS) at different times after surgery: 2, 4, 8 and 18hours. For the necessary sample size estimations, the pain measurement in 2hours postoperative will be considered as the primary response. The sample size will directly depend on the clinically relevant minimum difference between the 2hours average pain level of both groups. The following table provides sample sizes for different minimum difference values:

Table 1.- Total sample size necessary to differentiate the mean degree of pain and statistical power, assuming a standard deviation \pm 1.25 for a confidence level of 95% and a t test for independent samples.

Minimum difference to be detected in VAS	Effect size (d)	Power reached		
		70%	80%	90%
0,5	0,4 (medium)	158	200	266
1	0,8 (large)	42	52	68
1,5	1,2 (very large)	20	24	32

For example, assume a mean VAS pain level at 2hours equal to 5 and in the other group 6. That difference, assuming a deviation ± 1.25 , equals a size of effect $d = 0.8$, which is considered a large magnitude. If for the researchers 1 point of difference in pain is already relevant, a total of 52 patients (26 per group) are needed to detect the difference as significant with a power of 80%.

In some articles (Annand, Göçmen) standard deviations between 0.84 and 1.6 are reported in different groups of local anesthetics and in the measurement times closer to 2hours. For this reason, this level of variability has been assumed (± 1.25). For a minimum difference of the largest clinically relevant pain score, for example, 1.5 points (5 vs. 6.5 in the groups), a total size of only 24 cases (12 per group) would be sufficient under the same conditions above. However, such low sizes should be avoided due to possible problems in ensuring the normal distribution of the data and being able to apply parametric tests, such as the t-test.

LIMITATIONS

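### Allocation is called both random and consecutive, with no stated sequence, concealment or time of disclosure to theatre staff

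*Combined protocol and SAP*

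**What the plan says.** Study design states random assignment twice, the second time as "Patients will be assigned randomly to one group or another". In the same paragraph, the sentence on blinding reads "Patients will not know the group that they have been assigned consecutively". The section on sample size and statistical analysis opens with "The sample selection method foresees the consecutive allocation of patients to two groups" and does not mention randomisation. Population separately describes how patients enter the study: "The source and mechanism of subject selection is a convenience sample, with consecutive recruitment in our clinic".

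Blinding, according to Study design, extends to the patient and to the recovery and ward nurses who record VAS, opioid use, PONV and complications. The surgeon and the anaesthesia team are not listed.

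Procedure/Intervention introduces the two arms with "After the nasal intubation of the patient, the administration of the LA will proceed by the following routes" and then describes each arm in turn. For the study group, "the surgeon will proceed firstly with pre-incisional infiltration with lidocaine and adrenaline and secondly with pre-extubation infiltration with ropivacaine". Pharmacological Treatments gives the same pre-incision mixture to both arms and writes the remaining intraoperative treatment for all patients. Limitations places the ropivacaine after the operation is finished and before extubation.

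**The concern.** Two questions are left open.

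The first is whether the next assignment can be foreseen at enrolment. If staff follow the analysis section as worded, whoever obtains consent may know which group comes next. The comparison of 2-hour VAS would then lose its basis in randomisation. Blinded VAS recording does not help, because it protects the measurement of the outcome and not the choice of who enters each arm. A problem of this kind cannot be repaired once patients are enrolled.

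The second is when theatre staff learn the group. The plan sets out the procedure by arm from intubation onward without giving a time. If the team knows early, the few intraoperative decisions that leave discretion could be influenced. These include the use of remifentanil boluses, the rule "If abrupt drops of the NIBP will proceed to stop the TCI RMF" (which has no threshold for what counts as abrupt), and adjuncts withheld for contraindication. Most other intraoperative care is fixed by dose or rule, so this route is limited.

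**Working it through.** **1. The plan's own figure.** Inputs from the sample size section: difference 1 VAS point, SD 1.25, 95% confidence, 80% power, independent-samples t test. The effect size is d = 1/1.25 = 0.8. A two-sided t test at 5% with 1:1 allocation needs 26 per group, 52 in total, with power 80.7%. This matches the plan, and all nine cells of Table 1 reproduce. The sample size is not in question.

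**2. The wording, section by section.**

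| Section | Subject | Word used |
|---|---|---|
| Study design | assignment | random (twice) |
| Study design, blinding sentence | assignment | consecutive |
| Population | recruitment | consecutive |
| Sample size and analysis | allocation to two groups | consecutive |

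Only the Population entry concerns recruitment. The other two uses of *consecutive* are attached to assignment or allocation.

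**3. What is absent.** I looked through the whole document for a method of sequence generation, block size, stratification, a holder of the list, a concealment device and a time of disclosure. None is given, and nothing suggests that text was blacked out.

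**4. When the group is needed.** The pre-incision infiltration is the same in both arms, and the intraoperative regimen is common to all patients. The arms first differ at the ropivacaine infiltration, after surgery is completed. It follows that the team does not need the group before then, apart from the short time required to prepare the infiltration. This is an inference from the plan; the plan does not say it.

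**5. Foreseeability over 52 patients.** The assumed strategy is to guess the arm with fewer patients so far and toss a coin at a tie.

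- Strict alternation: every assignment after the first is known, 51/52.
- Simple random list: 50.0% correct.
- Known blocks of 4: the chance of a correct guess at positions 1 to 4 is 1/2, 2/3, 2/3 and 1. The mean is (0.500 + 0.667 + 0.667 + 1)/4 = 70.8%.
- Random blocks of 4 and 6: 69.0% by simulation (20,000 runs), for someone who tracks every earlier assignment.

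**6. Why a restricted list is still reasonable.** Under simple 1:1 randomisation of 52, the probability of exactly 26/26 is C(52,26)/2^52 = 0.11. The probability of a 20/32 split or worse is 0.13. Power at 20/32 is 78.6%.

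**7. Scale of a spurious shift.** The shifts below are assumptions and do not come from the documents. SE = 1.25 × √(2/26) = 0.347; df = 50; critical t = 2.009; critical difference = 2.009 × 0.347 = 0.70 VAS. With no true effect, the non-central t distribution (non-centrality = shift/SE) gives:

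| Assumed shift (VAS) | Shift/SE | Two-sided false-positive rate |
|---|---|---|
| 0 | 0 | 5.0% |
| 0.1 | 0.29 | 5.9% |
| 0.25 | 0.72 | 10.9% |
| 0.5 | 1.44 | 29.3% |

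**The case against.** The best defence is that *consecutive* is loose wording. Random assignment is stated twice, and the two words are compatible: patients taken in order of arrival can be assigned from a random list. The sentence in the analysis section begins by speaking of sample selection, which echoes Population, and the document repeats itself elsewhere. This reading is plausible, so the plan has not been shown to be non-random. Even so, the word is tied to allocation in two places, and someone working from the analysis section alone would find no instruction to randomise. The missing sequence and concealment remain missing under either reading.

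A second objection is that the figures prove nothing about this trial. Alternation is not written anywhere, and the VAS shifts are assumed. That is right; they give scale only.

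Third, consecutive recruitment with mostly objective criteria leaves less room to select patients. It narrows the opportunity but does not remove it, since consent can still be influenced and some criteria, such as ASA class, need judgement.

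Fourth, no section says that theatre staff learn the group early, and co-treatment is largely fixed. This stands, and it makes the timing of disclosure the lesser part of the point.

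Finally, blocks are more guessable than a simple list when earlier assignments are tracked. This is true. It is the price of reaching the planned 26 per group, and it is why block sizes should vary and stay undisclosed.

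**Conclusion.** The concern holds. The plan gives conflicting descriptions of allocation and supplies none of the detail that would settle them. Foreseeability ranges from about 50% correct guesses under a simple random list to 51 of 52 assignments known under strict alternation, depending on a procedure the plan leaves unstated. The size and direction of any resulting bias in 2-hour VAS cannot be derived from the documents. The planned 52 patients are unaffected. This should be corrected before enrolment; it does not show that the trial is non-random. The conclusion rests on reading *consecutive* as applying to allocation, as the text has it, and on the inference that both arms share the same planned care until the ropivacaine.

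**What to change.** In Study design and in the sample size and analysis section, replace the wording on consecutive assignment with 1:1 random allocation from a computer-generated list, for example permuted blocks of varying size that are not disclosed to the team. Keep *consecutive* for recruitment only, as in Population. State that the list is concealed in sequentially numbered opaque envelopes prepared by someone not involved in recruitment. State also that each envelope is opened only when surgery is complete, just before the pre-extubation step.

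This keeps enrolment and the shared part of the procedure free of knowledge of the group. It does not blind the team between the opening of the envelope and extubation.

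The cost is a change of wording, a set of envelopes, and ropivacaine available in theatre for every case. Doses, sample size and endpoint stay as they are.
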